Blood sample for ApoE4 genotyping	X																	Optional ApoE4 sampling is collected at screening but can be taken at any visit until the last study visit (Section 8.7)
					J	Phar	maco	kinet	ics ar	ıd Ph	arm	acody	ynam	ics				
Blood sample for ADA assessment				X		X								X		X		ADA assessment is performed on blood sample collected for PK assessments; D1 and D8 assessment is performed on the pre-dose sample
Lumbar puncture for CSF collection ^e			х											X				Lumbar puncture indicated for D-1 can be performed any time between D-8 and D-1 CSF biomarkers, and TB006 levels will be determined in CSF

AD = Alzheimer's Disease; ADA = anti-drug antibody; AE = adverse event; anti-HCV = hepatitis C virus antibody; ApoE4 = apolipoprotein E4; COVID = coronavirus disease; CRF = case report form; C-SSRS = Columbia Suicide Severity Rating Scale; CSF = cerebrospinal

fluid; D = Day; DSM-5 = Diagnostic and Statistical Manual of Mental Disorders, Fifth Edition; ECG = electrocardiogram; E/D = Early Discontinuation;

HBsAg = hepatitis B surface antigen; IgM anti-HBc = immunoglobulin M antibody to hepatitis B core antibody; IV = intravenous(ly); MMSE = Mini-Mental State Examination;

NINCDS-ADRDA = National Institute of Neurological and Communicative Disorders and Stroke –

Alzheimer's Disease and Related Disorders Association; NPI = Neuropsychiatric Inventory; PD = pharmacodynamic(s);

PK = pharmacokinetic(s); SAE = serious adverse event.

CONFIDENTIAL Page 24 of 101

a Visit days and procedures are allowed a window of \pm 2 days from Day 1 to End of Treatment.

Protocol TB006AD2102

Protocol Date and Version: 15 Oct 2021; v 3.0

b Applicable only for patients who discontinue early from the study.

- c The medical history assessed at the screening visit should include prior AD treatment assessment(s). Establishing the clinical diagnosis of AD should include use of criteria from the DSM-5 Criteria for Major Neurocognitive Disorder (previously dementia) (Section, 10.4, Appendix 4) and the NINCDS-ADRDA (Note: ADRDA is now the Alzheimer's Association) (Section 10.5, Appendix 5).
- d The Cognitive Drug Research battery is to be performed twice during the screening visit in both Part 1 and Part 2.
- e The lumbar puncture procedure is optional.

f

Protocol TB006AD2102

Protocol Date and Version: 15 Oct 2021; v 3.0

	.2a						St	udy I)rug	Adm	inistr	ation	Peri	iod				Notes

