	Screening D -28 to D -2	D -2ª	D-1ª	D1ª	D2-6ª	D8	D9-13ª	D15a	D16-20ª	D22ª	D23-27a	D29a	D30-34ª	D36 a	D64ª	D104ª	E/Db	
Outpatient visit			X											х	X	X	X	If the patient is not overnight confined on D -1 (see above), the D -1 visit will be an outpatient visit
Site to contact patient					X		X		X		X		x					Investigator or designee to telephone the patient between D2-6, D9-13, D16-20, D23-27, and D30-34
							Centr	al La	bora	tory	Asses	smei	nts			-		
Viral serology (HBsAg, IGM anti-HBc, anti-HCV, HIV) and COVID-19	Х				(c)			>										
Urine alcohol	X		X	0.7.								X		X				Locally performed at site
Drug screening	X		X									X		X				
Clinical laboratory tests (clinical chemistry, hematology, urinalysis)	X		X			X				X				X		X	X	
		*	Pharn	nacod	ynan	nic A	ssess	ment	s: Co	gniti	on Te	esting	g, MI	RI, BI	ood S	Sampl	les	
MMSE	X		X					X						X	X	X	X	
Clinical Dementia Rating scale			X	rá.				X						X	X	X	X	
Cognitive Drug Research System battery ^d	X		X			X		X		X		X		X	X	X	X	
NPI			X	G L										X	X	X	X	

CONFIDENTIAL Page 28 of 101

Protocol TB006AD2102

Protocol Date and Version: 15 Oct 2021; v 3.0

Table 2. Part 2	- Sche	dule	of A	ctivit	ies													
	, , , , , , , , , , , , , , , , , , ,						St	udy I	Orug	Adm	inistr	ation	ı Peri	iod				Notes
	Screening D -28 to D -2 ^a	D -2ª	D-1ª	D1ª	D2-6ª	BQ	D9-13ª	D15a	D16-20ª	D22ª	D23-27 ^a	D29a	D30-34ª	D36 a	D64ª	D104ª	E/D ^b	
Blood sample for PD assessment			X											X		X	X	Fluid biomarkers will be determined in plasma
								Stu	ıdy T	reatr	nent							
Study drug IV infusion				X		X		X		X		X						
						-		Pha	arma	cokin	etics	1						
Blood sample for PK assessment				X								X		X	X	X	X	Pre-dose and the end of infusion on D1 and D29; single sample on other days
Blood sample for ADA assessment				X										X		X		ADA assessment is performed on blood sample collected for PK assessments; D1 assessment is performed on the pre-dose sample
Blood sample for ApoE4 genotyping	X																	Optional ApoE4 sampling is collected at screening but can be taken at any visit until the last study visit (Section 8.7)

AD = Alzheimer's Disease; ADA = anti-drug antibody; AE = adverse event; anti-HCV = hepatitis C virus antibody;

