ApoE4 = apolipoprotein E4; COVID = coronavirus disease; CRF = case report form; C-SSRS = Columbia Suicide Severity Rating Scale; CSF = cerebrospinal fluid; D = Day; DSM-5 = Diagnostic and Statistical Manual of Mental Disorders, Fifth Edition; ECG = electrocardiogram; E/D = Early Discontinuation; HBsAg = hepatitis B surface antigen; IgM anti-HBc = immunoglobulin M antibody to hepatitis B core antibody; IV = intravenous(ly); MMSE = Mini-Mental State Examination; NINCDS-ADRDA = National Institute of Neurological and Communicative Disorders and Stroke – Alzheimer's Disease and Related Disorders Association; NPI = Neuropsychiatric Inventory;

PK = pharmacokinetic(s); SAE = serious adverse event.

CONFIDENTIAL Page 29 of 101

Protocol TB006AD2102

Protocol Date and Version: 15 Oct 2021; v 3.0

a Visit days and procedures are allowed a window of ± 2 days from Day 1 to End of Treatment.

- b Applicable only for patients who discontinue early from the study.
- c The medical history assessed at the screening visit should include prior AD treatment assessment(s). Establishing the clinical diagnosis of AD should include use of criteria from the DSM-5 Criteria for Major Neurocognitive Disorder (previously dementia) (Section, 10.3, Appendix 4) and the NINCDS-ADRDA (Note: ADRDA is now the Alzheimer's Association) (Section 10.4, Appendix 5).
- d The Cognitive Drug Research battery is to be performed twice during the screening visit in both Part 1 and Part 2.

e

Protocol TB006AD2102

Protocol Date and Version: 15 Oct 2021; v 3.0

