2.3.1 Risk Assessment

A standard battery of toxicology studies was conducted with TB006. The pivotal safety assessment was a 1 month GLP toxicology study in cynomolgus monkeys. Doses ranged from 10 to 200 mg/kg, and evaluation included clinical and laboratory observations, a 5 week recovery period, and full histopathology. No treatment related adverse findings were observed. Mild lymphoid hyperplasia occurred in males at the 10, 100, and 200 mg/kg dose levels, but based on mild severity, lack of dose dependency and historical test facility data from similar studies in cynomolgus monkeys, this finding was considered a species specific mild, reactive immune response and not an adverse toxicological finding. It is likely an immunogenicity reaction. No other findings were observed in this or any of the other toxicology studies.

TB006 is a first in class monoclonal antibody, therefore there are no known class adverse effects or risks to report from clinical studies. In general, risks associated with other monoclonal antibodies include allergic reactions such as hives or itching, flu like symptoms such as chills, fatigue, fever, and muscle aches and pains, nausea and vomiting, skin rashes and decreases in blood pressure. These effects have not been observed in preclinical studies to date. Other marketed IgG4 humanized monoclonal antibodies, such as natalizumab, eculizumab, and pembrolizumab, are used clinically. These antibodies largely target the immune system. There appears to be a spectrum of target-related negative effects when the total antibody dose gets too high. This pattern is not evident with TB006 in the preclinical toxicology profile, but will be closely observed in Phase 1 studies.

When performed correctly and according to industry standards, venipuncture complications are rare. However, even when properly performed, complications can include fainting, dizziness, hematoma, nerve injury, and arterial puncture or laceration. Blood draws and administration of the IV infusion in this study will be performed adequately trained medical staff to minimize any risk to patients.

Risks associated with a lumbar puncture can include headache, pain or numbness, bleeding, infection, puncture pain, and herniation. The lumbar puncture procedure will be performed by medical staff experienced with the technique and using aseptic techniques to minimize any risk to patients.

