3 OBJECTIVES AND ENDPOINTS

Table 3. Objectives and Endpoints

O	BJECTIVES - PART 1	ENDPOINTS
Pr	imary	
•	To determine the safety and tolerability of multiple doses of TB006	Safety endpoints, including the incidence of AEs and SAEs, clinical laboratory parameters, vital signs, ECGs, C-SSRS, and physical and neurological examinations, until Day 104 after the first TB006 dosing
•	To determine the PK profile of multiple doses of TB006	 PK parameters derived by noncompartmental analysis using the TB006 plasma concentration-time data, including, but not limited to and as appropriate: AUCtau: area under the concentration-time curve over a dosing interval Cmax: maximum observed plasma concentration tmax: time at which maximum plasma concentration occurs Ctrough: concentration at the end of a dosing interval t½: terminal elimination phase half-life CL: total clearance Vd: volume of distribution Extent of CSF distribution as estimated by TB006 CSF concentrations
•	To determine the maximum tolerated dose of multiple doses of TB006	Safety endpoints as above
•	To assess the immunogenicity of TB006 (production of anti-TB006 antibody)	Detection of anti-TB006 antibodies
•		Change from baseline through end of study on the Clinical Dementia Rating scale – Sum of Boxes total score

Protocol TB006AD2102

Protocol Date and Version: 15 Oct 2021; v 3.0

	 Change from baseline through end of study on the Cognitive Drug Research system battery score, composite scores and individual task measures Change from baseline through end of study on the MMSE score Change from baseline through end of study on the NPI score
--	---

OBJECTIVES - PART 2	ENDPOINTS
Primary	
To determine the clinical efficacy of TB006 in patients with mild to severe AD	Change from baseline through Day 104 on the Clinical Dementia Rating scale – Sum of Boxes total score
Secondary	
To determine the clinical efficacy of TB006 in patients with mild to severe AD	 Change from baseline through Day 36 on the Clinical Dementia Rating scale – Sum of Boxes total score Proportion of responders on the Clinical Dementia Rating scale – Sum of Boxes at Days 36 and 104 Change from baseline to Days 36 and 104 on the Cognitive Drug Research System Battery, composite scores and individual task measures Change from baseline to Days 36 and 104 on the MMSE score Change from baseline to Days 36 and 104 on the NPI score

Protocol TB006AD2102

Protocol Date and Version: 15 Oct 2021; v 3.0

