8.8 Immunogenicity Assessments

Antibodies to TB006 will be evaluated in plasma samples collected from all patients at the time points according to the SoA (Table 1 and Table 2). These samples will be tested by the sponsor or sponsor's designee.

Anti-TB006 antibodies will be determined on plasma samples collected for plasma PK determinations, and no additional blood samples need to be obtained.

Plasma samples will be screened for antibodies binding to TB006 and the titer of confirmed positive samples will be reported. Other analyses may be performed to verify the stability of antibodies to TB006 and/or further characterize the immunogenicity of TB006.

The detection and characterization of antibodies to TB006 will be performed using a validated assay method by or under the supervision of the sponsor. All samples collected for detection of antibodies to study drug will also be evaluated for TB006 plasma concentration to enable interpretation of the antibody data. Antibodies may be further characterized and/or evaluated for their ability to neutralize the activity of the study drug(s).

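### The protocol draws a PK sample but schedules no ADA test at the Early Discontinuation visit, so a Part 2 patient who leaves before Day 36 has no scheduled post-dose ADA result, and the SAP schedule may disagree

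*Protocol*

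**What the plan says.** Protocol Section 1.3, Table 2 (Part 2) marks the ADA row at D1, D36 and D104, with the note "ADA assessment is performed on blood sample collected for PK assessments; D1 assessment is performed on the pre-dose sample". Table 1 (Part 1) marks D1, D8, D36 and D104 and says that "D1 and D8 assessment is performed on the pre-dose sample". The E/D cell of the ADA row is blank in both tables.

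The PK row is marked at E/D in both parts. The Part 2 PK note reads "Pre-dose and the end of infusion on D1 and D29; single sample on other days", so one PK sample is due at E/D. A footnote defines the E/D column: "Applicable only for patients who discontinue early from the study".

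Protocol Section 8.8 ties ADA testing to the schedule tables, runs it on PK plasma, and states that "no additional blood samples need to be obtained".

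Immunogenicity is a primary objective of Part 1 (protocol Table 3). Part 2 lists no immunogenicity objective or endpoint. SAP 13.3 nevertheless tabulates ADA status and titer by treatment group in both parts, and by severity stratum in Part 2. It uses the Safety Analysis Set, which contains everyone who was randomized and dosed. It gives no rule for a dosed patient who has no post-dose ADA result.

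**The concern.** ADA is the only row in Tables 1 and 2 that is marked at D104 but not at E/D. Examinations, vital signs, ECG, adverse events, medications, C-SSRS, outpatient visit, laboratory tests, the cognition scales, NPI, PD blood and PK are all marked at both. No reason is given, so the blank looks like an oversight.

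The patients affected are those who leave early. Protocol Section 2.3.1 notes that "risks associated with other monoclonal antibodies include allergic reactions such as hives or itching". The SAP (Section 12.1) identifies an adverse event leading to discontinuation by withdrawal from the study. A patient counted there has left the study, and has no scheduled ADA test on leaving. Missing ADA status would therefore depend on early departure and possibly on the reason for it. Without a stated rule, a programmer could count such a patient as negative, leave the patient out of the denominator, or carry the D1 pre-dose result as the patient's status.

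**Working it through.** **1. Marks in the protocol schedules, read by column.**

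| Row | Marked at | E/D |
|---|---|---|
| Part 1 PK | D1, D8, D29, D36, D64, D104 | yes |
| Part 1 ADA | D1, D8, D36, D104 | no |
| Part 2 PK | D1, D29, D36, D64, D104 | yes |
| Part 2 ADA | D1, D36, D104 | no |

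**2. Sample counts in protocol Tables 6 and 7.**
- Part 1: six samples on each of D1, D8 and D29, plus one on each of D36, D64 and D104, gives 6 × 3 + 3 = 21. Adding E/D gives 22, the number in Table 6. Volume: 22 × 5 = 110 mL. Total: 75 + 3.5 + 110 + 2 + 18 = 208.5 mL, as stated.
- Part 2: two samples on each of D1 and D29, plus one on each of D36, D64 and D104, gives 2 + 2 + 3 = 7. Adding E/D gives 8, the number in Table 7. Volume: 8 × 5 = 40 mL. Total: 75 + 3.5 + 40 + 2 + 18 = 138.5 mL, as stated.

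Both PK/ADA counts are reached only with the E/D draw. This is supporting evidence only, because the same tables do not count E/D elsewhere. The six laboratory collections are screening, D-1, D8, D22, D36 and D104, and the three PD collections are D-1, D36 and D104. The direct evidence is the E/D mark in the PK row.

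**3. Scheduled post-dose ADA results for a dosed patient who leaves before D36.**
- Part 2: D1 is pre-dose and the next test is D36, so 0 results.
- Part 1: 1 result if the patient reached D8 (taken before the second infusion), otherwise 0.
- With ADA marked at E/D, each count rises by 1 for a patient who attends that visit. Draws stay at 22 and 8.

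**4. Possible size.** The documents give no dropout rate, so the rates here are assumptions. At 5%, 58 × 0.05 = 2.9; at 15%, 58 × 0.15 = 8.7. That is about 3 to 9 TB006 patients in Part 2 without a post-dose result. In Part 1, one patient is 1 of the 6 on TB006 in a dose group (17%).

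**5. What missing results do to a proportion.** Suppose 5 of 58 are untested and 3 of the other 53 are positive: 3/53 = 5.7%. The full-group proportion lies between 3/58 = 5.2% (no untested patient positive) and 8/58 = 13.8% (all five positive). The observed 5.7% lies inside that range, so the direction of any bias is not determined.

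**6. SAP Appendix I against the protocol.** The SAP copy of the Part 1 schedule has four ADA marks, as in the protocol. The SAP copy of the Part 2 schedule has four where the protocol has three. The last three sit in the same positions as the last three marks of the laboratory row of that table, which the protocol places at D36, D104 and E/D. The extra mark is therefore probably E/D. It is not certain, because the table as available has lost a column and its PD row also carries one mark more than the protocol.

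**The case against.** The strongest reply is that a blank cell does not mean that the sample can never be tested. Protocol Section 8.5 splits each PK sample to keep a back-up aliquot and lets PK samples be used for safety concerns that arise during or after the study. A reader might infer from the schedule that an infusion reaction which ends participation could never be linked to antibodies. The documents do not support that. What stands is that such testing is optional, and testing prompted by a reaction would itself be selective.

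Second, protocol Section 7 expects withdrawal to be uncommon and asks sites to keep safety visits through Day 104 where possible. A patient who only stops study drug and attends D36 or D104 has a scheduled result. This narrows the gap to patients who leave the study before D36. The proposed change recovers only those who attend the E/D visit.

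Third, the ADA summaries are descriptive, Part 2 has no immunogenicity endpoint, and Part 1 has the D8 sample and may replace early leavers. All of this is correct, and it limits the point to a minor one.

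Fourth, the SAP may already show the E/D test for Part 2. If so, the SAP and protocol disagree. Section 8.8 points to the protocol's own tables, so a site following the protocol would still have no scheduled test.

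**Conclusion.** The gap is real and minor. The protocol schedules a PK draw but no ADA test at E/D in both parts. This leaves a Part 2 patient who departs before D36 with no scheduled post-dose ADA result, and a Part 1 patient with at most one, taken after a single infusion. The SAP 13.3 tables would then lack ADA status selectively for early leavers, with no rule for presenting them. The SAP Part 2 schedule probably conflicts with the protocol; this should be confirmed on the source file.

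The estimate of about 3 to 9 Part 2 TB006 patients rests on an assumed 5% to 15% leaving the study before D36, for which the documents offer no figure.

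A reader might infer that reported ADA incidence is biased low. That would need untested patients to be counted as negative when some are positive, or leavers to be positive more often than those tested; the documents establish neither. The primary efficacy analysis does not use ADA status and is unaffected.

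**What to change.** - **Protocol Tables 1 and 2:** mark ADA at E/D, and extend the row notes to say that it is run on the PK sample drawn at that visit.
- **SAP Appendix I:** align the ADA row in both parts with the protocol, after checking what the extra Part 2 mark denotes.
- **SAP 13.3:** include E/D results in the ADA status table. Show dosed patients with no post-dose ADA result as a separate not-evaluable category, by treatment group, and do not count them as negative.

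The cost is one schedule mark per part, a few extra assays and two sentences in the SAP. No extra blood is needed, because the assay uses plasma already collected. The volumes of 208.5 mL and 138.5 mL do not change.

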2 INTRODUCTION

TB006 is a humanized IgG4 (S228P) type monoclonal antibody, being developed by TrueBinding, Inc. for the treatment of AD.

2.1 Study Rationale

The TB006 nonclinical pharmacology program establishes its potential as a therapeutic agent for AD by neutralizing Gal-3, which regulates the production and accumulation of $A\beta$ and tau proteins and is overexpressed in AD. The preclinical data have shown evidence of addressing underlying disease pathology and improving cognition.

The preclinical safety profile of TB006 further supports the clinical investigation of TB006.

This is a two-part Phase 1b/2a combined MAD and proof of concept study in patients with AD. Part 1 of the study will evaluate the safety, tolerability, PK, PD and efficacy of TB006, administered qw as an IV infusion over 1 hour. Part 1 of this study will be conducted in parallel with the Phase 1 SAD study (Protocol number TB006HV1101). Each dose level in this study will start after the safety, tolerability, and PK of the single dose equivalent to the combined total of the 5 qw doses has been established. In Part 2 of this study, enrollment will continue at the highest tolerated dose from Part 1. Part 2 will assess the efficacy of TB006 on cognition using the Clinical Dementia Rating scale – Sum of Boxes as the primary endpoint. Patients enrolled at the same dose level in Part 1, as well as all placebo patients, will be included in the efficacy analyses in Part 2. Randomization in Part 2 will be stratified according to patient severity.

This study will characterize TB006 safety, tolerability, plasma and CSF PK, and efficacy. In
addition, the effect of TB006 on CSF and plasma biomarkers
, as well as cognition, using the Clinical Dementia Rating Scale, the MMSE, the
Cognitive Drug Research system battery, and the NPI, will be evaluated.

2.2 Background

2.2.1 Disease Background

AD is a chronic progressive neurodegenerative disorder and is the leading cause of dementia among older adults. In the US, AD is one of the leading causes of death, ranking sixth among US adults and fifth among adults aged 65 years or older (CDC, 2020).

The most common and thoroughly investigated hypotheses proposed to explain the pathophysiology of AD are the amyloid hypothesis and tau hypothesis. Considerable evidence suggests that toxic changes in $A\beta$ and tau initiate the disease cascade. Abnormal tau accumulates to form neurofibrillary tangles inside nerve bodies, where they destroy cell structure and interfere with neuronal function and communication. Eventually, cell death and brain atrophy result.

Protocol TB006AD2102

Protocol Date and Version: 15 Oct 2021; v 3.0

Other factors that may also contribute to AD include insufficient blood and nutrient delivery of the vascular system to the brain and neuroinflammation which damages neurons in the brain.

Drug development in the dementia arena has been highly active in the past 20 years. There are approximately 5 compounds with market approval, all of which aim to improve the symptoms of dementia. These "symptomatic" treatments may improve cognition in the short term but have no effect on the progression of the disease. More recently, therapies with large molecule antibodies have explored the impact of targeting the underlying pathology such as amyloid or damaged tau. These treatments seek to modify the course of the disease by slowing disease progression. Although some of these compounds have shown efficacy in patient subtypes and have demonstrated an acceptable safety and tolerability profile in clinical studies (Panza et al, 2019; Van Dyck, 2017), none have met their primary endpoint; ergo none have been approved for marketing. Therefore, an urgent unmet medical need remains for the treatment of AD.

Key to the success of drug development in this patient population is the need to identify patients early in the course of their disease for treatment intervention. Patients with advanced symptomatic disease have significant demyelination, neuronal cell loss, and loss of volume. Early identification measures include advanced imaging, most notably MRI, CSF testing for the presence of abnormal A β and tau, and sensitive cognition testing (NIA, 2020; Risacher and Saykin, 2013).

